### **18.1.1. ALL AEs**

AE tables will be summarized by oral Lurasidone tablet period and double-blind injection period (dose level of Lurasidone injectable suspension and pooled placebo).

AE tables will be summarized by oral Lurasidone tablet period and double-blind injection period (dose level of Lurasidone injectable suspension and pooled placebo).

Injection site reaction related AEs summary tables and figure will be presented by ISAF population.

Listing of all AEs will also be presented by OSAF population..

#### **18.1.1.1. Severity**

- Severity for the oral Lurasidone tablet period is classed as mild/ moderate/ severe (increasing severity). AEs starting after the first Lurasidone tablet dose with a missing severity and ended during the double-blind injection period will be classified as severe

---

Document:

Author:

Version Number:  
Version Date:

Final Draft  
11APR2019

Template No: CS\_TP\_BS016 Revision 4  
Effective Date: 01Apr2016

Reference: CS\_WI\_BS005

during that period. If a subject report an AE more than once within that SOC/ PT, the AE with the highest case severity will be used in the corresponding severity summaries.

- Severity for the double-blind injection period is classed as mild/ moderate/ severe (increasing severity). AEs starting after the first Lurasidone injection dose with a missing severity will be classified as severe. If a subject report an AE more than once within that SOC/ PT, the AE with the highest case severity will be used in the corresponding severity summaries.

#### **18.1.1.2. Relationship to Study Treatment**

Relationship, as indicated by the Investigator, is classed as “not related”, “possible”, “probable” (increasing severity of relationship) or definite.

For summaries by relationship to the study drug, AEs will be grouped as “related” or “not related.”

- AE Related: AEs with relationship to study drug assessed as “possible,” “probable,” or “definite”
- AE not Related: AEs with relationship to study drug assessed as “not related”
- AEs with a missing relationship to study drug will be regarded as “related”

If a subject report the same AE more than once within that SOC/ PT, the AE with the strongest case relationship to study drug will be used in the corresponding relationship summaries.

#### **18.1.2. AEs LEADING TO DISCONTINUATION OF STUDY**

AEs leading to discontinuation of the study will be identified by using the AE page of the electronic case report form (eCRF), where “Caused Study Discontinuation” is answered as “Yes”.

Summary and Listing of AEs leading to discontinuation of the study, will be presented.

#### **18.1.3. SERIOUS ADVERSE EVENTS**

Serious adverse events (SAEs) are those events recorded as “Serious” on the Adverse Events page of the (e)CRF.

Summaries of SAEs will be provided.

---

Document:

Author:

Version Number:  
Version Date:

Final Draft  
11APR2019

Template No: CS\_TP\_BS016 Revision 4  
Effective Date: 01Apr2016

Reference: CS\_WI\_BS005

Listing of SAEs will also be presented.

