10.2.1. Pretreatment Events and Adverse Events

Pretreatment events will be recorded from the time informed consent is provided at screening until the time of first lurasidone oral tablet dose administration at Day -7.

Adverse events will be collected for each subject from immediately after the first lurasidone oral tablet dose administration at Day -7 until the follow-up visit at Day 61 (\pm 2).

Subjects should be queried in a non-leading manner, without specific prompting (eg, "Has there been any change in your health status since your last visit?"). See Section 11, Safety Reporting.

AEs and SAEs will be monitored throughout the study at all visits.

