10.5.2.1. Day -12 (Washout/Taper)

The following study-related procedures will be performed:

- Admit Subject to Clinical Site.
- Perform Physical Examination.
- Obtain Vital Signs.
- Perform 12-Lead ECG.
- Collect Blood Sample for b-hCG Serum Pregnancy Test (female subjects).
- Collect Urine Sample for:
 - Urine Drug Screen
 - Urine Alcohol Test
- Begin washout/taper of psychotropic medications (may begin Day -19).
- Provide Meals.
- Record Concomitant Medications.
- Record Pretreatment Events.

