11. SAFETY REPORTING

11.1. Definitions

11.1.1. Adverse Events

An AE is any untoward medical occurrence associated with the use of a drug in humans, whether or not considered drug related.

Untoward medical occurrences that occur between the time of signing the informed consent form (ICF) and drug administration are pre-treatment events. Those that occur after administration of study drug are considered AEs. Pre-treatment hospitalizations that occur in accordance with local clinical practice during the screening period (for wash-out from prior or concomitant medications) will not be considered as SAEs and do not need to be reported as such. Any untoward event that may occur during the hospitalization must be recorded as a pretreatment event. If hospitalization is prolonged by an untoward event, the event must be reported as an SAE.

An AE can, therefore, be any unfavorable and unintended sign (including an abnormal or clinically significant laboratory finding), symptom, or disease occurring after the administration of a medicinal (investigational) product, whether or not considered related to the medicinal (investigational) product. AEs may include the onset of new illness and the exacerbation of pre-existing conditions.

The Investigator should attempt to establish a diagnosis of the event based on signs, symptoms, and/or other clinical information. In such cases, the diagnosis should be documented as the AE and not the individual signs/symptoms.

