11.1.2. Serious Adverse Events

A serious adverse event (SAE) is pretreatment event or an AE that meets one or more of the following criteria:

- Results in death.
- Is life-threatening.
- Requires hospitalization or prolongation of existing hospitalization.
- Results in persistent or significant disability or incapacity.
- Is a congenital anomaly or birth defect.
- Is an important medical event that may jeopardize the subject or may require a medical or surgical intervention to prevent one of the outcomes listed above. Examples of such medical events include allergic bronchospasm requiring intensive treatment in an emergency room or at home, blood dyscrasias or convulsions that do not result in inpatient hospitalization.

The term "severe" is often used to describe the severity of a specific event (as in mild, moderate, or severe myocardial infarction) (see Section 11.3); the event itself, however, may be of

relatively minor medical significance (such as severe headache). This is not the same as "serious," which is based on subject/event outcome or action criteria usually associated with events that pose a threat to a subject's life or functioning as defined by the criteria above.

During the study, if a subject has a hospitalization or procedure (eg, elective surgery) that was scheduled before the study entry, ie, before informed consent for an event/condition that occurred before the study, the hospitalization is considered a therapeutic intervention and not the result of a SAE. However, if the event/condition worsens during the study, it should be reported as an AE (or SAE, if the event/condition results in a serious outcome such as prolongation of hospitalization).

Life-threatening means that the subject was, in the view of the Investigator, at immediate risk of death from the event as it occurred. This definition does not include an event that had it occurred in a more severe form might have caused death.

SAE criteria information will be captured on the CRF.

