11.3. Collection and Recording of Adverse Events

All pre-treatment events and AEs must be recorded in the subject's study records/source documents in accordance with the Investigator's normal clinical practice.

All pre-treatment events and AEs must be recorded on the CRF.

Pre-treatment events will be recorded from the time informed consent is provided at Screening until just prior to first lurasidone oral tablet study drug dose at Day -7. AEs will be recorded beginning after first study drug dose administration on Day 1 until the follow-up/study completion visit at Day 61 (\pm 2).

All AEs will be followed until resolution, stabilization of the condition, the event is otherwise explained, or the subject is lost to follow-up.

Each AE is to be evaluated for duration, severity, frequency, seriousness, action taken with the study treatment, outcome, and causal relationship to the study treatment. Definitions for severity, frequency, action taken with the study treatment, outcome, and causal relationship to the study treatment are presented below.

The severity of AE:

- **Mild** Ordinarily transient symptoms that do not influence performance of subject's daily activities. Other treatment is not ordinarily indicated.
- **Moderate** Marked symptoms sufficient to make the subject uncomfortable. Moderate influence on performance of subject's daily activities. Other treatment may be necessary.
- Severe Symptoms cause considerable discomfort. Substantial influence on subject's daily activities. May be unable to continue the study, and other treatment may be necessary.

The frequency of AE:

- Once an isolated episode.
- **Intermittent** occurs on two or more separate occasions.
- **Continuous** does not abate from date of onset to date of resolution.

The outcome of the AE:

- Recovered/Resolved
- Recovering/Resolving
- Not Recovered/Not Resolved
- Recovered/Resolved with Sequelae
- Fatal
- Unknown

The causal relationship of the AE to the study treatment:

Not related

o **Not related** – Improbable temporal relationship and is plausibly related to other drugs or underlying disease.

Related

- o **Possible** occurred in a reasonable time after study drug administration, but could be related to concurrent drugs or underlying disease.
- Probable occurred in a reasonable time after study drug administration, is unlikely to be attributable to concurrent drugs or underlying disease, and there is a plausible mechanism to implicate the study drug.

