#### **18.1. PRETREATMENT EVENTS AND ADVERSE EVENTS**

Pretreatment events will be recorded from the time informed consent is provided at screening until the Document:

Author:

Version Number:  
Version Date:

Final Draft  
11APR2019

Template No: CS\_TP\_BS016 Revision 4  
Effective Date: 01Apr2016

Reference: CS\_WI\_BS005

time of first lurasidone oral tablet dose administration at Day-7.

Adverse events will be collected for each subject from immediately after the first lurasidone oral tablet dose administration at Day -7 until the follow-up visit at Day 61 ( $\pm 2$ ). Adverse Events (AEs) will be coded using Medical Dictionary for Regulatory Activities (MedDRA) central coding dictionary, Version 21.0 or higher.

- Adverse Events for the Oral Lurasidone tablet period is defined as an AE that started on or after the first dose of the oral lurasidone tablet.
- Adverse Events for the double-blind Injection period is defined as an AE that started on or after the date of the double-blind injection.
- Adverse Events that started on the Oral Lurasidone tablet period and continued the double-blind injection, but the severity did not change the AE will be reported in the Oral Lurasidone tablet period. If the severity of the AE gets worse, the AE will be considered in the double-blind injection period.

AEs will be summarized by treatment and by MedDRA system organ class (SOC) and Preferred Term (PT).

An overall summary of number of subjects within each of the categories described in the sub-section below, will be provided as specified in the SAP.

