## Statistical Analysis Plan

PROTOCOL D1052024  
 Page 65 of 66

Number	Title
Listing 16.2.4.4	Listing of Prior and Concomitant Medications - Oral Safety Population
Listing 16.2.5	Listing of Study Drug Dispensing and Administration - Oral Safety Population
Listing 16.2.3	Listing of Data Excluded from the Pharmacokinetic Analysis and/or Reporting - Pharmacokinetic Population
Listing 16.2.6.1.1	Listing of Blood Pharmacokinetic Sample Collection Times and Serum Lurasidone and Metabolite Concentrations - Pharmacokinetic Population
Listing 16.2.6.1.2	Listing of Serum Lurasidone and Metabolite Concentrations Following Lurasidone Injection - Pharmacokinetic Population
Listing 16.2.6.1.3	Listing of Urine Pharmacokinetic Sample Collection Times and Lurasidone and Metabolite Concentrations - Pharmacokinetic Population
Listing 16.2.6.1.4	Listing of Individual Serum Lurasidone Pharmacokinetic Parameters - Pharmacokinetic Population
Listing 16.2.6.1.5	Listing of Individual Serum Metabolite Pharmacokinetic Parameters - Pharmacokinetic Population
Listing 16.2.6.1.6	Listing of Individual Amount and Fraction of Dose Excreted of Lurasidone in Urine by Collection Interval - Pharmacokinetic Population
Listing 16.2.6.1.7	Listing of Individual Cumulative Amount and Fraction of Dose Excreted of Lurasidone in Urine by Collection Interval and Renal Clearance - Pharmacokinetic Population
Listing 16.2.6.1.8	Listing of Individual Amount and Cumulative Amount Excreted of Metabolites in Urine by Collection Interval - Pharmacokinetic Population
Listing 16.2.6.2	Listing of Positive and Negative Syndrome Scale (PANSS) Questions - Pharmacodynamic Population
Listing 16.2.7.1	Listing of Adverse Events - Oral Safety Population
Listing 16.2.7.2	Listing of Serious Adverse Events or Death - Oral Safety Population
Listing 16.2.7.3	Listing of Adverse Events Leading to Early Discontinuation - Oral Safety Population
Listing 16.2.7.4	Listing of Psychiatric Hospitalization - Oral Safety Population
Listing 16.2.8.1	Listing of Urine Alcohol, Drug and Cotinine Screening Results - All Screened Subjects
Listing 16.2.8.2	Listing of Clinical Laboratory Measurements: Serum Chemistry - Oral Safety Population
Listing 16.2.8.3	Listing of Clinical Laboratory Measurements: Hematology - Oral Safety Population

Document:

Author:

Version Number:  
 Version Date:

Final Draft  
 11APR2019

Template No: CS\_TP\_BS016 Revision 4  
 Effective Date: 01Apr2016

Reference: CS\_WI\_BS005

Table Number	Table Title

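### The SAP's SAE outputs omit serious pretreatment events, so a serious washout event in a subject never given a tablet is in no planned event table or listing

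*SAP*

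**What the plan says.** **Protocol.** Section 11.1.2 defines the term: "A serious adverse event (SAE) is pretreatment event or an AE that meets one or more of the following criteria". Section 10.2.1 sets the window: "Pretreatment events will be recorded from the time informed consent is provided at screening until the time of first lurasidone oral tablet dose", which is given on Day -7. Section 11.1.1 says a planned washout stay is not itself an SAE, but adds: "If hospitalization is prolonged by an untoward event, the event must be reported as an SAE". Section 11.3 requires collection: "All pre-treatment events and AEs must be recorded on the CRF". It does not name the page.

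**SAP.** Section 18.1.3 states: "Serious adverse events (SAEs) are those events recorded as" serious on the Adverse Events page. Section 18.1.4 identifies fatal events from the outcome field on that page. Section 6.1.1 admits a subject to the Oral Safety Population only after at least one oral tablet. In Appendix 4, Listing 16.2.7.2 is titled "Listing of Serious Adverse Events or Death - Oral Safety Population". The listings of AEs, of AEs leading to discontinuation and of psychiatric hospitalization (16.2.7.1, 16.2.7.3 and 16.2.7.4) use the same population. Section 18.1 has pretreatment events in its title and repeats their recording window, and Appendix 2 assigns records to that class by date. No table or listing in Appendix 4 reports the class. Section 4.7 declares no change from the protocol's analyses or definitions.

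**The concern.** The incidence of SAEs is a stated safety endpoint in both documents. The protocol withdraws clinically stable subjects from their antipsychotics, so the washout is an exposure created by the study. Serious harm in that interval falls within the protocol's own SAE definition. If the SAP is programmed as written, some protocol-defined SAEs will be recorded on the CRF but will not appear in the study report's event outputs. A reader of those outputs could not tell whether there were no serious washout events or whether they were simply not listed.

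**Working it through.** No figure in the plan depends on this point, so the check is mainly a comparison of definitions, populations and outputs.

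**1. Does the washout fall inside the pretreatment window?** Protocol 10.5.2.1 starts the taper at Day -12, or as early as Day -19, and the period ends on Day -8. The first tablet is on Day -7. The washout therefore lies wholly inside the window:
- Day -19 to Day -8 inclusive: -8 - (-19) + 1 = 12 days.
- Day -12 to Day -8 inclusive: -8 - (-12) + 1 = 5 days.

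**2. Where could a serious washout event appear?**

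| Planned output | Subject never given a tablet | Subject later given a tablet |
|---|---|---|
| Table 14.3.2.1, SAEs (Safety Population) | No: outside the population | No: SAP Appendix 1 has oral, injection-dose and placebo groups only, and Appendix 2 classes a known start before the first tablet as not an AE |
| Listings 16.2.7.1 and 16.2.7.2 (Oral Safety Population) | No | Only if the event sits on the Adverse Events page |
| Listing 16.2.7.4, psychiatric hospitalization (Oral Safety Population) | No | Possible: no date limit is stated |
| Pretreatment-event table or listing | None planned | None planned |
| Medical history (SAP 12) | No: conditions must stop by Screening | No: same rule |
| Table 14.1.1 and Listing 16.2.1.1, disposition (all or all screened subjects) | Reason for leaving only | Only if the subject later leaves |

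**3. Which CRF page holds pretreatment events?** The documents point both ways. Protocol Tables 2 and 6 list pretreatment events and adverse events as separate items, which suggests separate pages. The AE algorithm in SAP Appendix 2 sorts records into one class or the other by date, which suggests a shared source. Neither settles it.

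**4. How many subjects could be affected?** Protocol 14.1 plans about 70 subjects overall and up to 40 injected (5 cohorts × 8 = 40, which agrees).
- Not injected: 70 - 40 = 30, and 30/70 = 43%.

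This is a ceiling. Subjects who fail oral tolerability have taken a tablet, and alternates held to fill a cohort may have done so too. The documents do not say whether the 70 are screened or enrolled. The number leaving before Day -7 is therefore between 0 and about 30.

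**5. Illustration under assumed risks.** The documents give no serious-event risk for the washout. For an assumed risk p per subject, the chance of at least one such event among n subjects never given a tablet is 1 - (1 - p)^n:

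| n | p = 1% | p = 2% | p = 5% |
|---|---|---|---|
| 10 | 9.6% | 18.3% | 40.1% |
| 30 | 26.0% | 45.5% | 78.5% |

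With n = 0 the chance is zero.

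**The case against.** **The protocol's analysis section is itself limited to events after dosing.** Protocol 14.3.5.1 defines the AEs for analysis as those on or after study medication and places the SAE summaries there. Its Safety population is randomized and dosed subjects, and the safety objective concerns the injection. The SAP goes further than this by adding an oral population. This stands for the tables: restricting Table 14.3.2.1 to post-dose events is reasonable, and its incidence figures are not biased. It does not justify redefining the SAE in SAP 18.1.3, or limiting the SAE and death listing to dosed subjects. Appendix 4 does not apply that limit everywhere: urine alcohol, drug and cotinine results are listed for all screened subjects.

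**Serious washout events do reach the sponsor.** Protocol 11.4.1 requires immediate reporting of every SAE, related or not. This also stands. The gap is in the planned outputs, not in detection or oversight.

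**Stronger readings that the documents do not support:**
- A reader might infer that washout deaths appear nowhere. Death and adverse event are termination reasons in Protocol 12.1, which also requires the date of death on the CRF. SAP 9 accounts for every consented subject. A death should appear in disposition, though no event term, seriousness criterion or causality is planned there.
- A reader might infer that serious washout harm is zero by construction in the SAE outputs. That is not shown for subjects who later take a tablet, because SAP 18.1.3 sets no start-date limit and the CRF page is unstated.
- A reader might take the whole period from Day -35 to Day -8 as washout: 28 of about 96 days, or 29%. The first 28 - 12 = 16 of those days precede the earliest taper.

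**Conclusion.** The concern holds in a limited form. The SAP's SAE definition is narrower than the protocol's. As planned, a serious washout event in a subject never given a tablet is in no SAE, AE or pretreatment-event output, and a death or withdrawal would show only as a disposition reason. For a subject later given a tablet, the SAE table has no place for the event, and its appearance in Listing 16.2.7.2 depends on the CRF page.

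The number of subjects concerned is unknown, from 0 to about 30 of about 70. The 43% is an upper bound and not an estimate. The documents give no washout event rate, so the probabilities above rest on assumed risks. SAE incidence after dosing and the dose-escalation decisions are unaffected. The point merits correction because a stated rule makes the SAE listing incomplete under the protocol's own definition.

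**What to change.** 1. Reword SAP 18.1.3 and 18.1.4 so that SAEs and fatal events follow Protocol 11.1.2 and draw on both pretreatment-event and AE records, whichever CRF page holds them.
2. Base Listings 16.2.7.2 and 16.2.7.4 on all consented (screened) subjects, with a period column: pretreatment, oral or injection.
3. Keep Table 14.3.2.1 for post-dose SAEs by treatment, and add a footnote giving the number of serious pretreatment events.

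The cost is SAP wording and a small amount of listing programming. No new data are needed, because Protocol 11.3 already puts these events on the CRF.

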#### **18.1.4. ADVERSE EVENTS LEADING TO DEATH**

AEs leading to death are those events which are recorded with an AE outcome of “Fatal” on the Adverse Events page of the (e)CRF.

#### **18.1.5. DURATION OF INJECTION SITE REACTION AEs FOR THE DOUBLE-BLIND INJECTION PERIOD**

The duration of the injection site reaction AEs is calculated as the AE end date minus the AE start date during the period from start of double-blind injection period (day 1) through follow-up visit date (day 61 +2). If the end date of the AE is missing, then the duration of the AE will be imputed using the last contact date for subjects who withdrew from the study, or the study completion date for subjects who completed the study. For subjects experiencing more than one occurrence of an AE, only the duration of the longest event will be summarized.

ISAF population will be used for the duration of AEs. The time (in days) to first AE in the double-blind Injection period and the duration (in days) of the AEs will be presented in tabular and figure format summarized by Lurasidone injection dose groups, all Lurasidone dose groups and pooled placebo. The following will be presented for the duration of AEs.

- Figure of the incidence of any post-injection AE by study day.
- Duration of all injection site reaction related AEs in Days by Treatment

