Randomized Subject	Any subject who was randomized into the treatment period of the study and was assigned a randomization number.
Enrolled Subject	Any subject who was successfully screened and enrolled into the pre-randomization period of the study.
Randomization Failures	Any subject who was enrolled but not randomized.
Completed Subject	Any subject who participated throughout the duration of the study, up to and including Day 29.
Early Termination Subject	Any subject who was successfully screened and randomized into the treatment period of the study, but did not complete the study.
End of Treatment	The day that the subject receives the protocol-defined last dose of the study drug.
End of Study	The day of the last visit by the last subject in the study.

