10.5.4.3. Day 33 (End of Restabilization)

The following study-related procedures will be performed:

- Awaken Subject.
- Provide Meals.
- Perform Physical Examination.
- Record Weight and BMI.
- Obtain Vital Signs (approximately time-matched to the injection predose timepoint on Day 1).
- Perform 12-Lead ECG (approximately time-matched to the injection predose timepoint on Day 1).
- Collect Blood and Urine Samples for Clinical Laboratory Tests (time-matched to the injection predose timepoint on Day 1):
 - Hematology
 - Serum Chemistry
 - Urinalysis
- Collect Blood Sample for Serum Prolactin.
- Administer C-SSRS (Since Last Visit version).
- Continue prior psychotropic medications.
- Record Concomitant Medications.

- Record Adverse Events.
- Schedule Next Visit.
- Discharge Subject.

10.5.5. Follow-up/Study Completion, Day 61 ± 2

All subjects will have an outpatient follow-up safety visit.

Subjects who discontinue the study after Day 29 but prior to Day 61 will undergo assessments scheduled for Day 61 at the time of discontinuation.

The following study-related procedures will be performed:

- Perform Physical Examination.
- Record Weight and BMI.
- Obtain Vital Signs.
- Perform 12-Lead ECG.
- Collect Blood and Urine Samples for Clinical Laboratory Tests:
 - Hematology
 - Serum Chemistry
 - Urinalysis
- Collect Blood Sample for Serum Prolactin.
- Collect Blood Sample for PK.
- Administer C-SSRS (Since Last Visit version).
- Record Concomitant Medications.
- Record Adverse Events.

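### Injection-site reactions unresolved at last contact are summarised as completed durations, and the SAP text asks for no ongoing count or flag

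*SAP*

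**What the plan says.** SAP 18.1.5 defines the duration of an injection-site reaction as end date minus start date, within a period that runs from the injection on Day 1 "through follow-up visit date (day 61 +2" days). When no end date is recorded, the rule for a withdrawn subject is "If the end date of the AE is missing, then the duration of the AE will be imputed using the last contact date"; the alternative is "the study completion date for subjects who completed the study". Where a subject has several occurrences, "For subjects experiencing more than one occurrence of an AE, only the duration of the longest event will be summarized". The output is Table 14.3.1.5, by treatment, in the injectable safety population.

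The section does not mention the AE outcome, although Protocol 11.3 collects one and "Not Recovered/Not Resolved" is among its categories. The AE tables in SAP Appendix 2 only assign events to periods; they do not deal with unresolved events.

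The documents give two signals on what counts as completion. Protocol Table 4 defines a completed subject as "Any subject who participated throughout the duration of the study, up to and including Day 29". The heading of Protocol 10.5.5 is "Follow-up/Study Completion, Day 61 ± 2", and Protocol 11.3 also places the study completion visit at Day 61.

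**The concern.** A reaction that is unresolved when the subject is last seen is right-censored: its duration is known only to be at least the time observed. The SAP rule turns that lower limit into an ordinary duration. In the summary, a subject last seen on Day 7 with an open reaction then looks the same as one whose reaction healed on Day 7.

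This matters somewhat for this product. Protocol 6.3.2 reports injection-site granuloma as the primary finding in dogs, with no no-observed-adverse-effect level. It describes findings that appeared within a week and persisted for another week before beginning to resolve. Persistence is therefore a fair question, and Table 14.3.1.5 is the planned by-dose summary of it. With six active subjects per dose, one misread value can move a group median.

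**Working it through.** The documents state no expected duration, non-resolution rate or withdrawal rate, so there is no planned figure to reproduce. What follows applies the SAP rule.

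**1. Values entered for an unresolved Day 1 reaction.** Entered value = day of last contact − 1. In-period maximum = 61 − 1 = 60 d (58 to 62 d with the ±2-day visit window).

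| Last contact | Entered | Possible understatement |
|---|---|---|
| Day 7 | 7 − 1 = 6 d | 0 to 60 − 6 = 54 d |
| Day 15 | 15 − 1 = 14 d | 0 to 60 − 14 = 46 d |
| Day 22 | 22 − 1 = 21 d | 0 to 60 − 21 = 39 d |
| Day 29 | 29 − 1 = 28 d | 0 to 60 − 28 = 32 d |

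The key date is last contact, which may be later than the day of withdrawal.

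**2. Completers.** A Day 1 reaction with no end date is entered as 61 − 1 = 60 d if study completion is the Day 61 visit, or 29 − 1 = 28 d if it is Day 29. On the Day 29 reading an unresolved reaction is understated by up to 60 − 28 = 32 d, a second source of downward error. On the Day 61 reading it has the in-period maximum but is not marked as ongoing.

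**3. Effect on a six-subject summary (assumed durations).** Take resolved reactions of 10, 14, 18, 22 and 30 d and one unresolved reaction with last contact on Day 7, entered as 6 d.
- SAP median = (14 + 18)/2 = 16 d; SAP mean = (94 + 6)/6 = 16.7 d.
- If the sixth reaction truly lasted 14 d or less, the median is still 16 d. At 18 d it is 18 d; at 22 d or more it is (18 + 22)/2 = 20 d. The median is therefore understated by 0 to 4 d.
- The true in-period mean, (94 + x)/6, runs from 16.7 d at x = 6 to 25.7 d at x = 60.

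**4. Censored instead of completed (assumed durations).** Four reactions resolve at 7, 10, 14 and 14 d; two are unresolved at last contact on Day 8, entered as 7 d each.
- SAP: mean = 59/6 = 9.8 d, median = (7 + 10)/2 = 8.5 d.
- Kaplan-Meier: survival is 5/6 after 7 d, 5/6 × 2/3 = 0.56 after 10 d and 0 after 14 d, so the median is 14 d.
- If last contact for those two is Day 15 instead, both medians are 14 d.

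**5. Longest-event rule (constructed case).** Pain from Day 1 to Day 6 resolves: 6 − 1 = 5 d. Pain from Day 8 is still open at last contact on Day 11: 11 − 8 = 3 d entered, with up to 61 − 8 = 53 d possible. The subject is summarised as 5 d and the open reaction leaves the table.

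**6. Likely size at plausible rates (illustration only).** Assume exponential durations with a 14 d median, a fraction p of subjects withdrawing uniformly over 1 to 27 d, and contact ending at withdrawal. The reported median t solves 0.5^(t/14) × [(1 − p) + p(27 − t)/26] = 0.5. For p = 5, 10 and 20% this gives 13.5, 13.0 and 12.2 d. The chance that a withdrawal precedes resolution is 0.535, so the expected number of affected reactions among six is 6 × p × 0.535 = 0.16, 0.32 and 0.64. The simulated SD of a six-subject median at 14 d is about 8 d.

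**The case against.** The best defence is that the rule assigns an ongoing reaction the longest duration the data support, and that little is lost in practice. Much of this stands.

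- Last contact need not be the withdrawal day. Protocol 11.3 follows AEs to resolution, stabilisation, another explanation or loss to follow-up, and early-termination subjects who received lurasidone are still restabilised. The values in step 1 are therefore tied to last contact.
- Resolution status is usually known. Subjects who stop before Day 29 have the Day 29 assessments at discontinuation, including the injection-site checks. This limits the problem, but it also shows that the information is available and the rule ignores it.
- A reader might infer that ongoing reactions are marked nowhere. The documents do not support that. SAP Appendix 2 keeps imputed dates out of the listings, so the end date should appear blank there. The investigator grades in SAP 18.6.1 show persistence up to Day 29. The table templates referred to in SAP section 8 may also carry a flag. The gap is in the text governing the duration summary.
- A reader might infer that the rule always shortens durations. It does not: a resolved reaction whose end date was never recorded is overstated when carried to study completion, although daily site checks to Day 15 probably make this uncommon.
- A reader might set the rule against SAP 18.1.1.1, where "AEs starting after the first Lurasidone injection dose with a missing severity will be classified as severe", and conclude that the SAP abandons a worst-case convention. The comparison is weak. Severity has a worst level; time beyond last contact has no observed one.
- Table 4 of the protocol defines who is a completed subject, not a completion date, and the period in SAP 18.1.5 points to Day 61. That reading is favoured, but it is not stated.

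**Conclusion.** The point holds, at a modest level. SAP 18.1.5 reports a known minimum as a completed duration whenever a reaction is unresolved at last contact, and its text requires nothing that would show this in Table 14.3.1.5. For a Day 1 onset and last contact between Day 7 and Day 29, the entry is 6 to 28 d against a possible 60 d. The undefined completion date adds a 28 d or 60 d ambiguity for completers.

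The actual size cannot be estimated from the documents. It is zero if every reaction has an end date, and under the assumptions in step 6 it is small beside the sampling variation of a six-subject median. A reader might also infer that dose escalation or a safety endpoint is compromised. That is not supported: the listed endpoint is the incidence of injection-site reactions, not their duration, and nothing ties the Safety Review Team's decisions to this table. This is a correction worth considering for one descriptive output.

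**What to change.** In SAP 18.1.5:
- Use the AE outcome to classify each reaction as resolved, or as ongoing at last contact or the Day 61 visit.
- State that the study completion date is the Day 61 visit, or reconcile the term with Protocol Table 4.
- Flag resolved events with an unknown end date separately from ongoing ones.

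In Table 14.3.1.5:
- Report by dose the number of subjects with any ongoing reaction, whichever of their events is longest.
- Mark imputed durations of ongoing reactions as minimum values with a plus sign.
- Keep those reactions in the duration summary, either as right-censored values with a Kaplan-Meier median or in the existing summary with the flag and ongoing count beside it.

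A resolved-only mean or median should not be the headline, because it drops long reactions. With 10, 14, 18, 22 and 30 d resolved and one completer ongoing at 60 d, the SAP summary gives a median of (18 + 22)/2 = 20 d and a mean of 154/6 = 25.7 d. The resolved-only figures are a median of 18 d and a mean of 94/5 = 18.8 d.

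The cost is a rewritten paragraph and slightly more programming for one table; no new data are needed. With six subjects per dose some Kaplan-Meier medians may not be estimable. The method also assumes that withdrawal is unrelated to how long the reaction would have lasted, so the ongoing count should always be shown with it.
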